In the SPACE treatment condition parents participate in 12 weekly parent-only sessions. In the CBT treatment condition children participate in 12 weekly child-only sessions. Parents of children assigned to CBT will meet with the child's therapist three times over the course of the treatment study, to be kept informed about their child's progress and provide helpful information to the therapist. Sessions can take place in person at the Yale Child Study Center or over secure video-link using the HIPAA approved Zoom software provided by Yale University. Participants will choose whether to have the sessions in person or over zoom and can elect to have some in person and some over Zoom. Youth and parents will be re-assessed after 6 treatment sessions (MID) and after the 12th session (POST). These assessments include the same procedures done at the first assessment, except the MID assessment does not include clinical interviews. After the 12th treatment session children will also undergo a second neuroimaging scan using fMRI. In both treatment conditions participants will be invited back for a follow-up visit 6-months from their initial appointment. At this appointment, these assessment procedures are the same as the MID assessment, but does not include a video-taped interaction or saliva sample.

Participants who are already enrolled will be invited to electronically complete an optional set of questionnaires related to their experiences during the COVID-19 pandemic (Please see Measures for list of questionnaires). This part of the study is completely optional. The questionnaires will be administered via the HIPAA-secure REDCap platform. Participants will receive \$15 when they submit the completed questionnaires.

Assessment Procedures:

Each of these three assessments (PRE, MID, POST) will be conducted in single sessions at our clinic by carefully trained independent evaluators (IE). Each assessment session will include collection of biological samples, behavioral observation, and self-report measures. During the youth interview, the parent will be administered the questionnaires and vice versa.

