NOTE: Is this research proposal designed to enroll children who are wards of the state as potential subjects?

Yes ☐ No ☒

8. Inclusion/Exclusion Criteria: What are the criteria used to determine subject inclusion or exclusion? Inclusion Criteria: Children must be a) 6-12 years old; and b) score below 2 on the Petersen Pubertal Development Scale; and c) meet DSM-5 diagnostic criteria for a primary anxiety disorder; and d) not have another mental illness more impairing than their most impairing anxiety disorder; and e) have an IQ of >80 to minimize neurobiological heterogeneity. Exclusion Criteria: Children will be excluded for any of the following: a) neurological disorders (including seizures), organic mental disorders, psychotic disorders, or pervasive developmental disorders; or b) show high likelihood of hurting themselves or others; or c) current psychosocial or psychopharmacological treatment. Stable doses of stimulant medications for ADHD will be permitted if parent and child, in consultation with the prescriber, agree to not make changes to dosage during the study period and to not administer the medication in the 24-hour period prior to pre-treatment and post-treatment MRI scans (MRI scans will be arranged on dates the child would not be taking a stimulant medication, in consultation with the prescriber and with agreement from the parent); or d) history of neurological illness or head injury with loss of consciousness > 5 minutes; or e) vision or physical disability that interferes with seeing stimuli presented briefly on computer screen and/or clicking a mouse button rapidly and repeatedly; or f) have contraindications for MRI scanning (e.g., metal implants, pacemakers, braces, claustrophobia, pregnancy, weight > 250 pounds).

Exclusion Criteria – Parent: Parents will be excluded for any of the following: a) pervasive developmental disorders, mental retardation, selective mutism, organic mental disorders, bipolar disorder, psychotic disorders, drug/alcohol abuse/dependence; b) <1 year living with the child prior to admittance; c) suicidal attempt in past 6 months. When a child is excluded, the parent is also excluded (unless as parent of another child); when a parent is excluded, the child will not participate.

9. How will **eligibility be determined, and by whom?**

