All parents who are interested in participating in this study will be administered a standardized telephone screen to ensure their child is experiencing anxiety problems and is eligible for MRI (including current psychiatric medications). The brief telephone screen will be completed by trained research assistants. If their child is experiencing anxiety problems and is eligible for MRI, the family will be scheduled for the Pre Assessment. After signing informed consent/assent forms, parents and youth will complete the ADIS: C/P. The purpose of the interview is to determine DSM-5 anxiety diagnoses and to rule out exclusionary diagnoses. The ADIS: C/P will be completed by one of the study's personnel. Cognitive testing administered by trained research personnel during the evaluation visit will be used to determine eligibility based on IQ. Eligibility will be determined after reviewing results of the ADIS: C/P and Pre Assessment with key study personnel at a staff meeting.

At the MRI visit, participants will again be given a thorough metal screening (Yale-MRRC MRI Safety Questionnaire) by trained research personnel to ensure that they are still eligible for the MRI (e.g., to rule out participants with a change in status of metal in the body, such as a child who recently got braces). At any time (during the phone screening prior to enrollment, or after enrollment in the study), the research personnel and the PI may determine that a participant is not fit to enroll in or continue in the study should they judge that it is in the participant's best interest to do so, if the participant begins a new medication or treatment that would change their eligibility, if they (or their parent) do not comply with the study plan, if they repeatedly miss appointments, if there is concern about their (or their parent's) ability to complete the interview and/or questionnaires validly and reliably, or for various other administrative reasons.

10. Risks: Describe the reasonably foreseeable risks, including risks to subject privacy, discomforts, or inconveniences associated with subjects participating in the research.

Interviews and questionnaires: Feeling upset when talking about anxiety or attending to anxious thoughts.

Behavioral Interactions: Temporary discomfort when discussing an issue on which child and mother disagree.

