To minimize risk relating to treatment: Changes in parents' behavior (e.g., reducing their accommodation of the child's anxiety) involves some risk of children feeling upset, becoming angry, or parents' experiencing anxiety. Every treatment session includes a review of the past week and query for any uncomfortable events. Any description of extreme exacerbation in parent or child anxiety; suicidal or self-injurious behavior; or other potentially harmful or dangerous event will be reviewed clinically and addressed. The therapists will report any such event immediately to the PI. Co-investigator [name] has many years of experience working with anxious children and their parents, including in multiple large scale clinical trials and will oversee the project closely. Upon consultation, a determination will be made about the most appropriate manner in which to intervene (e.g., alternative treatment, hospitalization, etc.), and the child or parent will be excluded from the study, as necessary.

To minimize risk relating to cognitive and behavioral tasks: Participants can stop the tasks at any time and are reminded of this prior to beginning them.

To minimize risk relating to MRI: All FDA guidelines for MRI scanning are carefully observed at the Yale MRRC and Yale BIC. All of the scans will be performed using an MRI scanner employing pulse sequences and hardware that have been approved by the FDA. The field strength is 3 Tesla and all relevant operating characteristics (RF power deposition, rate of change of the field gradients, coil design) fall within the limits of FDA guidelines.

Participants will be carefully screened to exclude those who may have metal in or on their bodies that cannot be removed. We conduct a thorough metal screening at both the phone screening and again at the beginning of the MRI visit to ensure that the participant's status is still safe for MRI scanning. Yale MRRC and Yale BIC rules strictly forbid staff from entering the magnet room carrying metal objects.

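### Staff may end a randomised child's place in the study, not only treatment; no POST scan is provided for afterwards, and the missing fMRI outcome is imputed with no missing-data sensitivity analysis

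*Combined protocol and SAP*

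**What the plan says.** **Removal.** Section I, item 9 (eligibility) provides that, before or after enrolment, "the research personnel and the PI may determine that a participant is not fit to enroll in or continue in the study". Grounds include "if the participant begins a new medication or treatment that would change their eligibility" and "if they (or their parent) do not comply with the study plan, if they repeatedly miss appointments". The item also lists the participant's best interest, doubt about valid completion of measures, and a catch-all for administrative reasons. The power is discretionary. It is worded by enrolment rather than randomisation, but it exempts no randomised child, and several grounds arise mainly during treatment.

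Section I, item 11 (Minimizing Risks) covers events reported in treatment sessions, beginning with "Any description of extreme exacerbation in parent or child anxiety". After clinical review, "the child or parent will be excluded from the study, as necessary". Item 12 has the PI and a co-investigator supervising the therapists weekly, so some of the deciders will know the arm.

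**Assessment.** Under Section I, item 4 (Research Plan), POST follows session 12, and "After the 12th treatment session children will also undergo a second neuroimaging scan using fMRI". The first scan follows the PRE assessment; none is described between the two. The 6-month visit is dated from the initial appointment and follows MID procedures, which have no clinical interviews. No scan is named for it.

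**Analysis.** Section I, item 13 defines the Aim 1 outcome as the difference in amygdala reactivity between parent-absent and parent-present scans. The arms are compared on POST means adjusted for PRE. Missing values, fMRI included, are filled by chained-equation multiple imputation; the variables used are not listed. The only alternative analysis is robust estimation for non-normality or outliers. No analysis set and no missing-data sensitivity analysis are stated.

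**The concern.** Both removal texts end the child's place in the study, and nothing separates that from stopping treatment. A family that stops before session 12 has no date for POST, so a scan that could have been obtained is lost. For a removed child the imputation can draw on PRE data and any later questionnaires, but on no scan after PRE.

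Some grounds, notably worsening and starting another treatment, can follow from how treatment is going. The lost POST values may then differ from what the observed data predict. Standard multiple imputation does not correct for that, and nothing in the plan would show how far the Aim 1 result depends on it. POST PARS and CGI ratings are lost for the same children.

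**Working it through.** The documents give no removal rate, standard deviation, effect size, significance level or power calculation, so there is no figure of the plan's own to reproduce. What follows is illustration.

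**Inputs**
- 226 children: enrolment target, Section III, item 1.
- Assumed: all 226 randomised 1:1 (113 per arm), two-sided 5% test, PRE-POST correlation 0.5, imputation from arm and PRE only, no true difference over all randomised children.
- d_S, d_C: share removed in SPACE and CBT (assumed).
- δ: deficit in SD, meaning how much higher the removed children's unseen POST reliance is than predicted (assumed; equal in both arms unless stated).

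**Formulas**
- Bias in the SPACE minus CBT contrast = d_C × δ_C − d_S × δ_S.
- SE = √[0.75 × (1/n_S + 1/n_C)], where n is the number observed per arm and 0.75 = 1 − 0.5².
- Error rate = 1 − Φ(1.96 − bias/SE) + Φ(−1.96 − bias/SE).

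**Example: SPACE 5%, CBT 15%** (113 × 0.05 ≈ 6 v 113 × 0.15 ≈ 17 children)
- n_S = 107.35 and n_C = 96.05, so SE = √[0.75 × (1/107.35 + 1/96.05)] = 0.122.
- δ = 0.5: bias = 0.10 × 0.5 = 0.05 SD; error rate 7.0%.
- δ = 1.0: bias = 0.10 × 1.0 = 0.10 SD; error rate 13.0%.

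The approximation was checked by simulation (8,000 trials per scenario, 20 imputations, Rubin's rules):

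| Removal, SPACE / CBT | Deficit (SD) | Bias (SD) | Error rate, approximation | Error rate, simulated |
|---|---|---|---|---|
| 10% / 10% | 0.5 | 0 | 5.0% | 4.7% |
| 10% / 10% | 1.0 | 0 | 5.0% | 5.0% |
| 5% / 10% | 0.15 | 0.008 | 5.0% | 4.8% |
| 5% / 10% | 0.5 | 0.025 | 5.5% | 4.9% |
| 5% / 10% | 1.0 | 0.05 | 7.0% | 6.9% |
| 5% / 15% | 0.15 | 0.015 | 5.2% | 5.0% |
| 5% / 15% | 0.3 | 0.03 | 5.7% | 5.7% |
| 5% / 15% | 0.5 | 0.05 | 7.0% | 7.0% |
| 5% / 15% | 1.0 | 0.10 | 13.0% | 12.5% |

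Deficits of 0.15 and 0.3 SD stand for 30% carry-over of a 0.5 or 1.0 SD clinical deficit to the fMRI measure. Reversing the 10-point gap reverses the sign: simulated bias −0.050 and −0.098 SD, with the same error rates.

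Equal removal is not enough by itself; the deficit must also be equal. With 10% removed per arm and a 0.5 SD deficit in one arm only, the bias is 0.10 × 0.5 − 0.10 × 0 = 0.05 SD in size.

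**Precision when both are balanced.** SE with everyone followed = √(0.75 × 2/113) = 0.1152. With 10% removed per arm it is √(0.75 × 2/101.7) = 0.1214, a ratio of 1.054. Simulated power for a true 0.35 SD effect falls from 85.1% to 81.7%.

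**The case against.** The strongest reply is that this is discretionary participant-protection wording in an eligibility section, and that the effect is small even on the figures above. Much of that stands.

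- **The illustration leans upward.** Every removed child carries the deficit, though missed appointments or administrative removals need not track outcome. If a third of removals carried a 1.0 SD deficit, the 15% v 5% bias would be 0.10 × 1/3 = 0.033 SD and the error rate about 5.9%.
- **Fewer than 226 may be randomised**, since consent precedes the diagnostic interview and IQ testing. At an assumed 80 per arm the 13.0% becomes 10.6%.
- **Questionnaires could help the imputation.** The plan does not rule out MID or 6-month scores. The 6-month visit is not tied to session 12, but whether removed families are invited is not stated, and it restores neither the scan nor the interview-based ratings.
- **Aim 1 concerns target engagement.** A scan after new medication answers a somewhat different question, so the handling of such scans must be stated.

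The wording also protects children, and any change must keep the best-interest ground for ending assessments. None of this supplies a POST visit after removal or a check on the imputation assumption.

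Three stronger readings are tempting:
- A reader might infer that the gap favours SPACE. The documents do not show which arm would lose more.
- A reader might take "when a parent is excluded, the child will not participate" (Section I, item 8) as another removal rule. It closes the parent entry criteria and is not written for randomised families.
- A reader might infer that the Aim 2 analysis is biased. No Aim 2 model is given, so only the loss of POST PARS and CGI data can be claimed.

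**Conclusion.** The gap is plain in the text: the stated rules let recoverable POST outcomes of randomised children go uncollected, on grounds that can track outcome, and the plan has no check on the imputation that replaces them. Its effect is unknown in size and direction and probably small. The false-positive rate is about 5% to 7% under moderate assumptions. About 13% requires a threefold imbalance in removal together with a 1.0 SD deficit on an fMRI difference score, and should not be read as the expected case. All these figures rest on assumed removal rates, deficits, correlation and numbers randomised. The point merits a change because a POST scan not taken cannot be recovered later and the remedy is inexpensive.

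**What to change.** 1. **Section I, items 9 and 11.** For randomised children, make non-compliance, missed appointments, new treatment, administrative reasons and clinical worsening grounds to stop study treatment only. Assessments end on withdrawal of consent or assent, or when the PI judges further assessment unsafe or against the child's best interest. Measures that a family cannot complete validly may be omitted.
2. **Section I, item 4.** Set a POST window by date, for example 12 to 16 weeks after randomisation, whether or not sessions are completed. Offer POST ratings and questionnaires to every randomised child, and the scan where the child is MRI-eligible.
3. **Section I, item 13.** Analyse by assigned arm, as the arm coding there implies. Include MID and 6-month questionnaire scores in the imputation model. Report Aim 1 with and without scans taken after new psychotropic medication. Add a delta-adjusted sensitivity analysis that shifts imputed POST values by 0 to 1.0 SD, separately by arm, and report the shift at which the conclusion changes.
4. **Records.** Log and report the date and reason of each treatment stop, by arm.

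**Cost.** A few sentences in items 4, 9, 11 and 13. At an assumed 5%, 10% or 15% removal, about 11, 23 or 34 POST visits would be offered that would otherwise be lost (226 × 0.05, 0.10, 0.15). Section V, item 2 pays $100 for the second MRI visit plus $50 for completing all components. If all were attended in full, payments would be 11, 23 or 34 × $150 = $1,650, $3,450 or $5,100, for visits already planned. The delta-adjusted analysis needs no new data.

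**Downside.** Some families will decline, and POST data after other treatment reflect assignment plus that treatment, which the report must say.

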Cross-species neurobiological evidence indicates that parental presence reduces amygdala reactivity and activates the mPFC to reduce offspring anxiety. In humans we recently demonstrated parental presence increases functional connectivity between their child's mPFC and amygdala, reducing the child's amygdala reactivity and anxiety. In a healthy sample, parental engagement of child amygdala-mPFC connectivity was linked to the child's reliance on parents for help with anxiety. Data from clinically anxious children likewise show parental presence engages child mPFC, and data we collected since our previous submission demonstrate that parental presence reduces amygdala reactivity in clinically anxious children. Parental reduction of child anxiety via amygdala-mPFC circuitry serves an important function for children, but can go awry in childhood anxiety disorders. Evidence suggests that in typically developing children normative changes during frontoamygdala development correspond to a natural shift from child dependence on parents for anxiety reduction toward increased independent engagement of amygdala-mPFC circuitry and reduced amygdala reactivity. This shift toward independent anxiety reduction is impeded in clinically anxious children, whose symptoms are linked to a clear pattern of amygdala hyperactivity and deficits in prefrontal control of the amygdala.

Neurobiological and clinical research support this model, whereby clinically anxious children are more dependent on parents for amygdala-mPFC engagement and anxiety reduction. Data from clinically anxious children who requested their parent be in the scan room show significant impact of parental presence on the mPFC. Clinically, children with anxiety disorders rely heavily on parents, who are deeply embroiled and enmeshed in their child's anxiety symptoms through the process of family accommodation, defined as changes in parental behavior to help their child to avoid or alleviate anxiety.

4. Research Plan:

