Attention Bias to Threat. Attention bias to threat will be assessed with a probe-detection task using the computer software Eprime. Participants (both mother and child) will complete tasks using a provided laptop computer and mouse. A centered fixation cross will appear first and will be followed immediately by two faces of the same actor expressing different emotions, one above the other. Participants will be told that a probe (< or >) will appear on the screen and that their task is to push the corresponding mouse button

Blood Samples:

Subjects will be asked to provide us with a small blood sample for our research during the initial appointment, and again at the 6-month follow up appointment. The total amount drawn will be less than one ounce each time. An experienced and qualified professional will draw the blood from a vein near the elbow.

We will also ask for permission to store blood samples for future research projects. If the subject agrees, the blood will be stored in a safe place without personal identification and retained for future research purposes.

Saliva Sample

To collect a sample of saliva we will subjects to chew on a small cotton swab for about one minute, then spit it out into a special sterile container.

MRI:

All participants will be scanned using a 3T scanner located at the Yale Magnetic Resonance Research Center or Yale's Brain Imaging Center. We train children on the tasks in a simulator so that they can acclimate to the scanning environment. Prerecorded scanner sounds will be played as the participant is in the simulator. We will describe and answer any questions the child or parent has about the MRI procedure. The simulator is a replica of the 3T scanner and includes speakers for simulating sounds, a screen to simulate visual stimuli, and a motorized table for simulating experiences the participant will have in the actual scanner. The participant

will watch videos and practice the computer tasks while in the simulator. Only after acclimating the child to the scanner environment so that both the child and parent are comfortable with the procedure, will the child be scheduled for the actual scan. Otherwise the study will be terminated.

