- d. For multi-site studies for which the Yale PI serves as the lead investigator: N/A
 - i. How will adverse events and unanticipated problems involving risks to subjects or others be reported, reviewed and managed? Write here
 - ii. What provisions are in place for management of interim results? Write here
 - iii. What will the multi-site process be for protocol modifications? Write here

13. Statistical Considerations: Describe the statistical analyses that support the study design. General Overview. Data management protocols will be used to ensure data integrity. Missing values (including fMRI data) will be estimated using chained equation multiple imputation algorithms.¹⁰⁸ Analyses will focus on least squares test (OLS) of means and modern robust estimation procedures⁹⁴ that rely on Wilcox's R routines (which generally have more statistical power than traditional OLS)⁹⁵. If non-normality or outliers appear problematic, we will use the Wilcox functions base on M estimation. We will examine associations between arm and baseline variables to ensure successful randomization. Our analytic approach follows NIH guidelines on rigor and reproducibility, including analysis of sex as a potential covariate. Aim 1: Demonstrate target engagement. Child reliance on parent for amygdala reactivity reduction (calculated as the difference between amygdala reactivity to fear faces in the parent-absent compared to parent-present scan, and from hereon referred to as 'child reliance on parent') will decrease significantly from PRE to POST treatment for children whose parents participate in SPACE, as compared with children whose parents participate in CBT. The assessments of interest for this question are PRE and POST. The additional time-point (MID) will be useful to gain preliminary insights relating to more complex questions of mediation. The OLS analysis is a

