2-group single degree of freedom contrast between SPACE and CBT using child reliance on parent at PRE as a covariate to increase statistical power. The single degree of freedom contrast focuses on the comparison of covariate-adjusted means at POST. Of interest is whether the contrast between arms is statistically significant for child reliance on parent; the direction of change will be determined by the sign of the parameter estimates. A dummy variable for the two arms (SPACE, CBT) will be included in the OLS analysis, with randomization to SPACE scored 1 and randomization to CBT scored 0. A statistically significant negative parameter estimate of the effect of treatment arm on child reliance on parent indicates that reduction in child reliance on parent at POST is significantly greater following SPACE compared with CBT. The same analysis will be conducted for mPFC activation and for amygdala-mPFC functional connectivity.

SECTION II: RESEARCH INVOLVING DRUGS, BIOLOGICS, RADIOTRACERS, PLACEBOS AND DEVICES

If this section (or one of its parts, A or B) is not applicable, check off N/A and delete the rest of the section.

A. RADIOTRACERS ☒ N/A

B. DRUGS/BIOLOGICS ☒ N/A

B. DEVICES ☒ N/A

SECTION III: RECRUITMENT/CONSENT AND ASSENT PROCEDURES

1. Targeted Enrollment: Give the number of subjects:

- a. Targeted for enrollment at Yale for this protocol: 226 children and their mothers, for a total of 452 participants
- b. If this is a multi-site study, give the total number of subjects targeted across all sites:

Write here:

2. Indicate recruitment methods below. Attach copies of any recruitment materials that will be used.

- ☒ Flyers ☒ Internet/web postings ☐ Radio ☐ Tabling
☐ Posters ☐ Mass email solicitation ☐ Telephone
☒ Letter (postcard) ☒ Departmental/Center website ☐ Television
☐ X Blog posting with approved messaging/advertising
☐ Newsletter via email
☐ X messaging/advertising on music-listening platforms
☐ Medical record review* ☒ Departmental/Center research boards ☐ Newspaper
☒ Departmental/Center newsletters ☒ Web-based clinical trial registries ☒
 Clinicaltrials.gov
☒ YCCI Recruitment database
☒ Other: The Yale Child Study Center Anxiety & Mood Disorders Program sees children with anxiety disorders and those who meet study criteria will be offered the opportunity to

participate in the study. ☒ Social Media (Twitter/Facebook):

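### The Aim 1 model adjusts only for PRE reliance; prespecifying age, sex and scanner, and keeping each child on one scanner, would gain some precision at little cost

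*Combined protocol and SAP*

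**What the plan says.** All references are to the combined protocol and SAP.

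- **Outcome (Section I, item 13).** Child reliance on parent is "calculated as the difference between amygdala reactivity to fear faces in the parent-absent compared to parent-present scan", so it is a within-child difference at each visit.
- **Model (same item).** POST reliance is compared between arms by OLS with an arm dummy and PRE reliance: a "contrast between SPACE and CBT using child reliance on parent at PRE as a covariate to increase statistical power". The same model is then applied to mPFC activation and to amygdala-mPFC connectivity.
- **Other covariates.** The overview mentions only sex, "including analysis of sex as a potential covariate", with no rule for including it. Age and scanner do not appear.
- **Estimator.** The overview says "Analyses will focus on least squares test (OLS) of means and modern robust estimation procedures", and then: "If non-normality or outliers appear problematic, we will use the Wilcox functions base on M estimation". No criterion for that switch is given.
- **Development (Section I, item 3, Background).** In typically developing children, "normative changes during frontoamygdala development correspond to a natural shift from child dependence on parents" towards independent regulation. The next sentence says that this shift is impeded in clinically anxious children.
- **Age and sex.** Eligibility is 6-12 years with a pubertal score below 2 (Section I, item 8). Both variables are taken at the telephone screen (Section III, item 5).
- **Scanner (Section I, item 4, MRI).** "All participants will be scanned using a 3T scanner located at the Yale Magnetic Resonance Research Center or Yale's Brain Imaging Center". I found no rule tying a child's scans to one scanner.
- **Order of events (Section I, item 4).** The text places randomisation after the PRE assessment and appears to place the first scan after randomisation. Section III, item 3 gives the same order for assessment and randomisation but does not mention the scan.

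**The concern.** The plan gives power as its reason for including PRE reliance. The same reason applies to any other baseline variable that predicts POST reliance. Age is the obvious candidate, since the protocol's own model of the outcome is developmental and the enrolled range spans seven years of age. Sex is left undecided. Scanner may add variance in two ways: children on different scanners may differ in measured reactivity, and a child who changes scanner between PRE and POST may have a less informative PRE value.

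What is at stake is the width of the confidence interval for the target-engagement contrast, and for the two further imaging outcomes that share the model.

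**Working it through.** **The plan's own figure.** Target enrolment is 226 children (Section III, item 1). It cannot be reproduced, because the documents state no alpha, power, effect size, SD, PRE-POST correlation or dropout. I use 226 only as a base, and assume 113 per arm, two-sided 0.05, no loss, and a starting power of 80%.

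**Gain from added covariates.** Let R² be the share of the variance remaining after arm and PRE reliance that the added covariates explain. The documents give no value, so a range is assumed.

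- Standard error ratio = √(1 − R²)
- Equivalent sample size = 226 / (1 − R²)
- Power = Φ[(1.960 + 0.842) / √(1 − R²) − 1.960]

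| Assumed R² | SE ratio | Equivalent N | Extra children | Power |
|---|---|---|---|---|
| 0.02 | 0.990 | 230.6 | 4.6 | 80.8% |
| 0.05 | 0.975 | 237.9 | 11.9 | 82.0% |
| 0.10 | 0.949 | 251.1 | 25.1 | 84.0% |

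**Cost of the extra terms.** The planned model has three coefficients (intercept, arm, PRE reliance), leaving 226 − 3 = 223 residual degrees of freedom. Age, sex and one scanner indicator reduce this to 220. Chance imbalance in three added covariates raises the expected variance of the arm coefficient by about 3/220 = 1.4%, or roughly 226 × 0.014 ≈ 3 children. So at R² = 0.02 most of the gain is used up (4.6 − 3.1 = 1.5 children); at 0.10 most of it remains (25.1 − 3.1 = 22).

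**Scanner and the difference score.** Write A and P for parent-absent and parent-present reactivity at one visit.

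- Additive shift c, both scans on one scanner: (A + c) − (P + c) = A − P. The shift cancels.
- Additive shift c, with the two scans on different scanners: the difference becomes A − P ± c. It does not cancel.
- Scale factor k: kA − kP = k(A − P). It does not cancel, and a change of scanner from PRE to POST puts the two visits on different scales.

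A scanner term absorbs a difference in mean reliance between scanners. It does not repair a scale difference. For that, keeping a child on one scanner is the more useful step, because it at least puts that child's PRE and POST values on one scale. The documents give nothing from which to size either effect.

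**Is scanner a baseline variable?** Age and sex are fixed before randomisation. If the PRE scan follows randomisation, the choice of scanner may too. Adjusting for it is safe only if the choice does not depend on arm.

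**The case against.** The case for leaving the model alone is strong on several points.

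- **Age may add little.** The Background statement concerns typically developing children, and the protocol says the shift is impeded in the children it enrols. The pubertal limit narrows the developmental range. PRE reliance already carries much of any stable age effect. All of this stands, and it is why the gain is shown as an assumed range and may lie near the bottom of it.
- **Scanner switching is inferred from silence.** Nothing says that children change scanner, one set of acquisition parameters is listed, and an additive shift cancels when both scans of a visit share a scanner. This also stands. A reader might infer a large loss of PRE-POST correlation from scanner changes; the documents give no correlation and no switching rate, so no such figure can be supported.
- **The Aim 1 analysis is largely specified.** Outcome, contrast, arm coding, covariate and OLS are all stated. That is right. What remains open is whether sex enters, and what would trigger the move to M-estimation.

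None of this argues against fixing, in advance, a short list of covariates already in the data, or against a scheduling rule. It limits how much they can be expected to return.

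**Conclusion.** The point holds as an inexpensive, optional improvement in precision. Under an assumed R² of 2-10% beyond PRE reliance, it is worth about 5-25 children on 226, or about 1-4 power points from 80%, before a cost of about 3 children for the extra coefficients. The result rests on that assumed range, equal arms, two-sided 0.05 and no loss.

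Three stronger readings are tempting, and the documents do not support them.

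- **That omitting age or scanner biases the comparison or inflates type I error.** It does neither in a randomised contrast.
- **That the fallback to M-estimation breaks error control.** The stated trigger is distributional shape, not the result. In 4,000 simulated null trials of 226 children per error type, switching to a Huber M-estimate on a residual normality test rejected in 4.9% of trials with normal errors and 4.8% with t errors on 4 degrees of freedom (Monte Carlo standard error about 0.3 points). Rates of about 6-7% appeared only when the better of several p-values was taken, which the plan does not propose.
- **That the baseline check distorts the analysis.** The plan says "We will examine associations between arm and baseline variables to ensure successful randomization". Examining associations cannot ensure randomisation, but the text sets no threshold and no consequence for the model, so no harm to Aim 1 follows.

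**What to change.** In Section I, item 13:

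1. State the primary Aim 1 analysis as OLS ANCOVA of POST reliance on arm, PRE reliance, age (continuous), sex and a scanner indicator. For a child who has to change scanner, define beforehand which visit's scanner the indicator records. Use the same covariates for mPFC activation and connectivity.
2. Always report the M-estimate as a sensitivity analysis, in place of switching to it when the data look problematic.

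In Section I, item 4 (MRI):

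3. Where feasible, scan each child on the same scanner for both the parent-present and parent-absent conditions and at both PRE and POST. Record the scanner used at each visit.
4. Since the PRE scan appears to follow randomisation, state that the scanner is assigned without regard to arm, preferably by staff unaware of it or before allocation is known.

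The cost is a few sentences, three degrees of freedom and some scheduling flexibility. Age and sex are already collected; scanner needs only to be recorded.
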